2.3 Study Endpoints

Primary outcome endpoints:

- Number and severity of solicited local adverse events of all severities from first product administration through day 7;
- Number and severity of solicited general AEs and clinically significant hematological and biochemical laboratory abnormalities from first product administration through day 28;
- Number and severity of unsolicited adverse events from first product administration through end of study;
- Occurrence of serious adverse events from first product administration through end of study.

Secondary outcome endpoints

- Serum pharmacokinetics at each dose level through end of study by ELISA;
- Percentage of transmission reducing activity at different time points by SMFA.

Exploratory outcome endpoints

- Anti-drug antibody (ADA) levels in study subjects after receiving study product through end of study;
- An integrated population pharmacokinetic-pharmacodynamic model by Monte Carlo simulations.

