9.2 AEs, SAEs and SUSARs

9.2.1 Adverse events (AEs)

Adverse events are defined as any undesirable experience occurring to a subject during the study, whether or not considered related to the investigational product. All adverse events reported spontaneously by the subject or observed by the investigator or his staff will be recorded. Abnormal laboratory findings (e.g. clinical chemistry or hematology) or other abnormal assessments that are judged by the investigator to be clinically significant will be recorded as AEs (or SAEs if they meet the definition). The investigator will exercise his or her medical and scientific judgment in deciding whether an abnormal laboratory finding or any other abnormal assessment is clinically significant. If there are any severe complaints, the volunteer will be evaluated immediately by a qualified clinician using the appropriate clinical assessments according to standard hospital care.

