9.4.3 Recording of adverse event data collection

Study staff will train subjects on use of memory aid booklets for self-assessment of solicited local and general adverse events through 7 days (day of mAb TB31F administration and subsequent 6 days) post- administration of study mAb TB31F; and for self-assessment of adverse events and concomitant medications until day 28. Study staff will review and discuss with the subject all recorded events to ensure appropriate documentation and scoring prior to transferring of the diary card record to the eCRF.

If known, the trial clinician will record the diagnosis (i.e., disease or syndrome) rather than component signs, symptoms and laboratory values. If the signs and symptoms are considered unrelated to an encountered syndrome or disease they should be recorded as individual AEs. If a primary AE is recorded, events occurring secondary to the primary event should be described in the narrative description of the case (e.g. primary AE = Orthostatic hypotension; secondary event may be fainting, head trauma, etc.). In case of hospitalizations for surgical or diagnostic procedures, the pre-existing condition should be recorded as the SAE, not the procedure itself.

All adverse events/reactions (solicited and unsolicited), noted by the investigators will be accurately documented in the case report form by the investigators. For each event/reaction the following details will be recorded:

1. Description of the event(s)/reactions(s)
2. Date and time of occurrence
3. Duration
4. Intensity
5. Relationship with the intervention
6. Action taken, including treatment
7. Outcome

In addition, symptoms will be ranked as (1) mild, (2) moderate, (3) or severe, depending on their intensity according to the following scale:

Mild (grade 1): awareness of symptoms that are easily tolerated and do not interfere with usual daily activity

Moderate (grade 2): discomfort that interferes with or limits usual daily activity

Severe (grade 3): disabling, with subsequent inability to perform usual daily activity, resulting in absence or required bed rest

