9.5.4 Safety holding rules

The study may be placed on safety hold at any time for the following reasons:

- On advice of the safety monitor;
- On advice of the Principal/Clinical investigators;
- On advice of the SMC;
- On advice of the accredited METC;
- If holding rules are met (see below).

Holding rules for within-group progression:

If either of the first two subjects within a group meet a holding rule (see below), administration of TB31F will be held for all remaining subjects in that dosage group (and subsequent groups). The following stopping rules apply to subjects within a group:

- One or more participants experience a SAE that is determined to be at least possibly related to the administration of TB31F
- Two or more subjects experience a grade 3 adverse event (local, clinical systemic or laboratory systemic) possibly, probably or definitely related to TB31F administration and persisting at grade 3 for >48 hours

The study site member first aware of the event meeting the holding rule will notify the Principal Investigator and the Local Safety Monitor. The PI will alert the appropriate parties. The SMC will be notified within 24 hours. An ad hoc SMC review will be performed. The following considerations must be discussed:

- Relationship of the AE or SAE to the study product
- Relationship of the AE or SAE to TB31F dose
- If appropriate, additional screening or laboratory testing is provided to other subjects to identify subjects who may develop similar symptoms
- If any study related SAE is not listed on the current informed consent form (ICF), the PI will revise the ICF and subjects will be asked to provide consent on the new ICF

TB31F administration to subjects within the affected group and to the next higher dosage group may resume only if the local safety monitor, PI, SMC and the sponsor agree it is safe to resume TB31F administration. If the accredited METC has recommended safety hold, re-initiation of the study will require METC concurrence. The accredited METC and PATH REC will be informed of a safety hold by the sponsor. Following discussion, it may be decided to terminate the study.

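### Section 9.4.3 sends events secondary to a recorded AE to the case narrative, with no exception for a more severe or distinct event, and this is not reconciled with the rule to grade and assess every AE.

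*Protocol*

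**What the plan says.** Protocol section 9.4.3 contains three instructions on what becomes an AE record.

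- A known diagnosis is recorded in place of its component signs, symptoms and laboratory values. As the exception, "If the signs and symptoms are considered unrelated to an encountered syndrome or disease they should be recorded as individual AEs".
- Where a primary AE is recorded, "events occurring secondary to the primary event should be described in the narrative description of the case". The example is "primary AE = Orthostatic hypotension; secondary event may be fainting, head trauma, etc".
- The next paragraph is general: "All adverse events/reactions (solicited and unsolicited), noted by the investigators will be accurately documented in the case report form by the investigators". It continues "For each event/reaction the following details will be recorded", and the list that follows includes intensity and relationship with the intervention.

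Elsewhere, section 9.2.1 states: "All adverse events reported spontaneously by the subject or observed by the investigator or his staff will be recorded". Section 9.4.4 obliges the investigators to assess causality for each AE and SAE. Section 9.2.3 defines an SAE by its outcome or consequence, without limiting it to primary events, and requires all SAEs to be reported.

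The outputs that depend on these records are:

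- the primary endpoint in section 2.3, "Number and severity of unsolicited adverse events from first product administration through end of study";
- the grade 3 percentages in section 10.1;
- the SMC report contents in section 9.5.3;
- the grade 3 holding rule in section 9.5.4, which begins "Two or more subjects experience a grade 3 adverse event" and also requires at least a possible relationship and persistence at grade 3 for more than 48 hours;
- the SAP's safety outcome analyses, which count unsolicited events by ICD-10 type, grade and relationship.

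The SAP has no rule for secondary events.

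**The concern.** Recording a diagnosis instead of its symptoms is normal practice and is not at issue. The secondary-event sentence goes further, because it covers downstream consequences. Head trauma after a fall is not part of orthostatic hypotension. It has its own severity, its own duration and its own ICD-10 code.

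A site that follows this sentence could describe such an event in free text and believe it had complied. Tables and listings are built from AE records, so an event without a record would be absent from the unsolicited AE counts, the grade 3 percentages and the severity summaries that the SMC reviews between groups. Leaving out a record can only lower the number of AEs or the highest grade shown. With five subjects per group and safety as the primary objective, one such event is visible in the results.

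**Working it through.** **1. The passages side by side**

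| Question | Secondary-event sentence (9.4.3) | General rules (rest of 9.4.3, 9.2.1, 9.4.4) |
|---|---|---|
| Where does the event go? | Narrative of the primary case | Recorded as an AE in the case report form |
| Own intensity and relationship? | Not stated | Yes, for each event |
| Exception if more severe, or a separate medical event? | None | Not needed, because all AEs are recorded |

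The sentence does not say that the narrative is the sole place of recording. The contrast with unrelated signs and symptoms, which do get individual records, makes that the natural reading. If the general rules prevail, the secondary-event sentence misleads. If the specific sentence prevails, an event can lose its own grade and causality. The documents do not settle it.

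Two nearby provisions do not close the gap. Section 9.4.3 adds a new description when an AE changes in intensity, but this concerns the same AE and not a different consequence. Neither document says whether the primary AE takes the grade of its worst consequence.

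**2. The plan's own safety figure** (protocol section 4.4, n = 20)

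- At least one event at a true rate of 10.87%: 1 − (1 − 0.1087)^20 = 0.8999. The plan says 90%.
- No events at a true rate of 0.52%: (1 − 0.0052)^20 = 0.9010. The plan says 90%.

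Both reproduce, and neither is in dispute. They take for granted that an event that occurs is counted.

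**3. What one missed grade 3 event does** (assumed count; exact Clopper-Pearson intervals, the exact two-sided 95% CI being what section 10.1 calls for)

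- Zero events: upper limit = 1 − 0.025^(1/n). For n = 5 this is 52.2%; for n = 25 it is 13.7%.
- One event: lower limit = 1 − 0.975^(1/n), which is 0.5% for n = 5 and 0.1% for n = 25. The upper limit p solves (1 − p)^n + n·p·(1 − p)^(n−1) = 0.025, which gives 71.6% and 20.4%.

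| | Event has its own record | Event in narrative without a record |
|---|---|---|
| One dose group | 1/5 = 20% (0.5 to 71.6%) | 0/5 = 0% (0 to 52.2%) |
| All subjects | 1/25 = 4% (0.1 to 20.4%) | 0/25 = 0% (0 to 13.7%) |

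**4. Effect on the chance of seeing an event** (assumed shares)

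Suppose a share s of the events of interest sat in narratives without a record. The chance of counting at least one in 20 subjects at a true rate of 10.87% is 1 − (1 − 0.1087·(1 − s))^20.

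- s = 0: 90.0%
- s = 25%: 81.7%
- s = 50%: 67.3%

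The documents give no value for s. These figures show direction and scale only.

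**5. Holding rule**

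If two subjects each had a related grade 3 event lasting more than 48 hours, and one of these had no record of its own, the count would be 1 and not 2. One brief event would not meet the rule however it was recorded.

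**The case against.** The strongest reply is that the text never says secondary events go ungraded, unassessed or uncounted. A reader might infer that, but the per-event rule in the same section, together with sections 9.2.1 and 9.4.4, points the other way. This stands: the defect is an unreconciled conflict, not a stated loss of data.

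Other stronger readings also fail.

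- **Serious consequences are lost.** Section 9.2.3 covers any untoward occurrence that meets a seriousness criterion. A head injury requiring hospitalization is an SAE, and if at least possibly related it meets the first holding rule by itself.
- **The orthostatic hypotension example must be tabulated at grade 1 or 2.** Table A3 grades a measured systolic pressure, whereas the severity scale in section 9.4.3 is functional. An investigator could grade a disabling case as grade 3.
- **The grade 3 holding rule is disabled.** It needs two or more subjects, a relationship to TB31F and more than 48 hours at grade 3.
- **The statement in section 13.2 that groups 1-4 had no grade 3 AEs or SAEs is unsafe.** No document shows that a secondary event occurred. Table 5 lists feeling faint as a blood-sampling risk, but a faint could itself be the primary AE.
- **The SMC never sees narratives.** Section 9.5.3 sets minimum report contents and does not exclude them.

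It is also fair to say that one record per causal chain avoids counting a case several times in groups of five. Linking the records answers this. None of these replies says how a non-serious secondary event that is distinct, or more severe than the primary AE, is to be recorded.

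**Conclusion.** The point holds in a limited form. Section 9.4.3 gives a specific instruction that conflicts with its own per-event rule and with sections 9.2.1 and 9.4.4. On its natural reading, a non-serious secondary event that is a separate medical event, or of higher grade than the primary AE, may have no AE record. It would then be missed in the primary endpoint on number and severity, the grade 3 tabulation, the SAP counts and the SMC summaries.

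The possible bias runs towards fewer or milder AEs. Its size cannot be estimated from the documents. One missed grade 3 event, an assumed count, would change a group's rate from 20% to 0% and the study rate from 4% to 0%. The conclusion assumes that sites follow the specific sentence over the general one, and that tables are built from AE records. It does not show that any event has been missed. The correction should still be made, because it is cheap and bears on the primary safety data.

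**What to change.** 1. **Protocol section 9.4.3.** Reconcile it with sections 9.2.1 and 9.4.4 by adding: a secondary event that is serious, is of higher grade than the primary event, or is a distinct medical event (for example an injury) is recorded as its own AE or SAE with its own grade, causality and dates, and is linked to the primary event. Lesser consequences stay in the narrative.
2. **SAP, safety outcome analyses.** State that subject-level percentages count each subject once, at the highest grade, and that linked events are flagged in event counts so that one case is not read as several unrelated ones.
3. **Before database lock.** Check any existing narratives against this rule and add records where it requires them.

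The cost is a sentence or two in each document and a short review covering at most 25 subjects. The downside is a few more AE records, all linked.

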9.4.4 Assessment of causality

The investigators are obliged to assess the relationship between study procedures and the occurrence of each AE/SAE. The investigators will use clinical judgment to determine the relationship. Alternative causes, such as natural history or the underlying diseases, concomitant therapy, other risk factors and the temporal relationship of the event will be considered and investigated. The relationship of the adverse event with the study procedures will be categorized as:

Definitely: administration of the IP is the cause, another etiology causing the adverse event is not known.

Probable: administration of the IP is the most likely cause: however, there are alternative reasonable explanations, even though less likely.

Possible: there is a potential association between the event and administration of the IP, however, there is an alternative etiology that is more likely.

Unlikely: a relationship to the administration of IP is unlikely, however, it cannot be ruled out.

Not related: a relationship to the administration of the IP cannot be reasonably established; another etiology is known to have caused the adverse event or is highly likely to have caused is.

When a regulatory authority requests a binary classification (related vs. unrelated), definitely, probably and possibly related are considered to be “related”, while not related and unlikely related are considered to be “unrelated”. Thus, an intervention-related AE refers to an AE for which there is a possible, probable or definite relationship to the study intervention. The investigator will use clinical judgment to determine the relationship.

9.4.5 Follow-up of adverse events

All AEs will be followed until they have abated, or until a stable situation has been reached. AEs that result in a subject's withdrawal from the study or that are present at the end of the study will be followed up (if the volunteer consents to this) until a satisfactory resolution or stabilization occurs, or until a non-study related causality is assigned. Depending on the event, follow-up may require additional tests or medical procedures as indicated and/or referral to the general physician or a medical specialist. AEs and SAEs will be reported until end of study within the Netherlands, defined as the last patient visit.

9.5 Safety Monitoring Committee

9.5.1 Local safety monitor

For this study, a local safety monitor will be appointed, who will be involved in the review of severe and serious adverse events and volunteer safety. He/she is independent of the sponsor and the investigator. The local safety monitor is notified of all grade III adverse events probably or definitely related to TB31F administration and persisting at grade 3 for >48 hours.

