Escalation to the next higher dosage group will be dependent upon no safety signals arising as outlined in section 9.5.4 and will follow the same staggered algorithm as shown in figure 3. The SMC will review the safety data up to day 7 before proceeding to the next dosage group. The data to be reviewed before each dose escalation group includes the safety data (solicited and unsolicited AEs through day 7 post TB31F administration; see section 9.5.4) and clinically significant laboratory tests collected at 24 hours, 2 and 7 days following TB31F administration for all subjects in the specified dose group.

The decision to proceed at these defined time points to the next dosing group will be made by the study team upon the recommendation of the Safety Monitoring Committee (SMC) after reviewing the clinical and safety lab data available. Safety follow-up and collection of serum samples for pharmacokinetic and pharmacodynamic measurements will be done at following times: 0 hours, end

of infusion (EOI), 1, 3, 6 and 24 hours after product administration, and on days 2, 7, 14, 21, 28, 56 and 84 after product administration. Extra follow-up visits 4 and 10 days after administration for collection of serum/plasma for pharmacokinetic and pharmacodynamic measurements will be performed in group 5 (section 8.3.18). All subjects will be followed for approximately 84 days after mAb TB31F administration.

Table 1. Study groups

Study groups	Number of subjects	Single Dose	
		Mtb31F	Administration Route
Group 1	5	0.1 mg/kg	intravenous
Group 2	5	1 mg/kg	intravenous
Group 3	5	3 mg/kg	intravenous
Group 4	5	10 mg/kg	intravenous
Group 5	5	100 mg	subcutaneous

[figure not shown]

Figure 3 – Staggered dosing trial design for monoclonal antibody TB31F administration

For group 1, all subjects will receive a single dose of TB31F with a window of at least 48 hours. For groups 2-5, subject 1 and subject 2 will receive a single dose of TB31F with a window of at least 48 hours. Subjects 3, 4 and 5 of the same group will receive the same dose of mAb TB31F minimally 48 hours after subject 2. Escalation to the next dosage group will occur if no Group Holding Rules are met and upon review by the SMC.

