Subjects within a dosage group are to receive a single TB31F administration following a schedule, such that the first subject (sentinel) in each group will be administered mAb TB31F and observed for the occurrence of any AEs. The 2nd subject in each dose group will receive their dose of TB31F no sooner than 2 days after the first subject has received TB31F. For group 1, each remaining subject will receive their TB31F dose no sooner than 2 days after the previous subject. For groups 2-5, the remaining three

subjects in each dosage group will receive their TB31F dose no sooner than 2 days after the second subject has been administered TB31F. For the three remaining subjects in each dosage group, there will be at least a one hour interval in administration of TB31F between the completion of TB31F administration in one subject before the next subject is administered TB31F. On condition no holding rules are met (see below), administration of TB31F to all subjects within each dosage group will continue without any external (SMC) review. If a holding rule is met, administration of TB31F drug product will be held for all remaining subjects in that dosage group until the SMC has completed its review and made a recommendation on trial progress.

Inter-group progression

Progression to the next dosage group will depend in all cases upon a positive review by the SMC of safety data of the previous dosage group. The data to be reviewed before each dose group includes the safety data (solicited and unsolicited AEs through day 7 post TB31F administration) and clinically significant laboratory tests collected at 1, 2 and 7 days following TB31F administration for all subjects in the specified dose group. The SMC will review the AEs (local, general, and laboratory) and will make recommendations regarding the continuation of the study for each group.

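### The grade 3 notice rule for the local safety monitor (9.5.1) leaves out possibly related events, which the holding rule (9.5.4) counts

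*Protocol*

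**What the plan says.** Protocol section 9.5.1 appoints a local safety monitor, independent of sponsor and investigator, "who will be involved in the review of severe and serious adverse events and volunteer safety". It then states a notice rule: the monitor is "notified of all grade III adverse events probably or definitely related to TB31F administration and persisting at grade 3 for >48 hours". Section 9.4.3 defines the grade in question as "Severe (grade 3): disabling, with subsequent inability to perform usual daily activity".

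Section 9.5.4 has two holding rules. One concerns serious events at least possibly related to TB31F and needs one participant. The other needs two or more subjects with a grade 3 event "possibly, probably or definitely related to TB31F administration and persisting at grade 3 for >48 hours". The lead-in to these rules, however, begins "If either of the first two subjects within a group meet a holding rule", which can be read as letting a single sentinel suffice. Once a rule is met, 9.5.4 requires notice to the principal investigator and the local safety monitor, and notice to the SMC within 24 hours.

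Section 9.4.4 counts possible, probable and definite relationships as related to the intervention.

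On spacing, the text to Figure 3 in section 3 says: "For groups 2-5, subject 1 and subject 2 will receive a single dose of TB31F with a window of at least 48 hours" and "Subjects 3, 4 and 5 of the same group will receive the same dose of mAb TB31F minimally 48 hours after subject 2". Table 2 gives 2 days as both the optimal and the shortest allowed interval. Subjects 3 to 5 may follow one another after one hour. Section 9.5.3 says that, if no holding rule is met, "administration of TB31F to all subjects within each dosage group will continue without any external (SMC) review".

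**The concern.** The monitor can advise a hold at any time (9.5.4) and is the independent person to whom 9.5.1 directs notice of individual events. Within a group there is no SMC review unless a holding rule is met. The planned SMC review comes after all five subjects have at least 7 days of follow-up. An event that already counts as half of a two-subject rule is one the monitor should hear about, and 9.5.1 does not require that when the investigator rates it as possible.

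That rating could well arise here. Section 9.4.4 uses it when another cause is more likely, and every subject receives clemastine and paracetamol before dosing. Section 13.2 already points to clemastine as a known cause of fatigue, the most common general solicited event (12 of 20 subjects, grade 1 or 2). A ready alternative explanation favours a rating of possible over probable.

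What is at stake is group 5, the first subcutaneous use of the product.

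**Working it through.** **1. The two rules side by side**

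| Element | Notice to monitor (9.5.1) | Holding rule (9.5.4) |
|---|---|---|
| Grade | 3 | 3 |
| Persistence at grade 3 | >48 h | >48 h |
| Causality | probable, definite | possible, probable, definite |
| Subjects | each event | two or more (the lead-in is ambiguous) |

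The two rules share grade and duration. They differ in causality by exactly one category, and 9.4.4 places that category under related.

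**2. What follows for a first event that is non-serious, grade 3, possibly related and longer than 48 h**

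- *Two-subject reading of 9.5.4.* The event counts as one of two. The rule is not yet met, so 9.5.4 triggers no notice. The event is not probable or definite, so 9.5.1 requires none. It is not serious, so the 24-hour route in 9.2.3 does not apply. A second qualifying event meets the rule, and the monitor and SMC are then told. Notice of the first event is late, but the hold still happens.
- *One-subject reading for a sentinel.* The event itself meets the rule and 9.5.4 requires notice. There is no gap.

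**3. Timing, which bears only on the optional extra**

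Inputs: minimum gaps from section 3 and Table 2, administration time ignored. Subjects 1 to 5 are dosed at D = 0, 48, 96, 97 and 98 h.

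An event in subject i starting t hours after dosing (t ≥ 0) has lasted more than 48 h only after D_i + t + 48. For that to come before subject j is dosed, t < D_j − D_i − 48.

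| Event in | Before dosing | Onset must be under |
|---|---|---|
| Subject 1 | Subject 2 | 48 − 0 − 48 = 0 h (impossible) |
| Subject 1 | Subject 3 | 96 − 0 − 48 = 48 h |
| Subject 2 | Subject 3 | 96 − 48 − 48 = 0 h (impossible) |
| Subject 2 | Subject 4 | 97 − 48 − 48 = 1 h |
| Subject 2 | Subject 5 | 98 − 48 − 48 = 2 h |

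So at the minimum gaps, if an event in subject 2 starts 2 h or more after dosing, all five subjects may have been dosed before 9.5.1 requires notice of it. Longer gaps relax this hour for hour: the limit for the next dose is under 54 − 48 = 6 h at a 54 h gap, and under 72 − 48 = 24 h at a 72 h gap.

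If notice were instead given within 24 h of onset (an assumption, borrowed from the SAE rule), a 48 h gap would cover onsets up to 48 − 24 = 24 h after dosing.

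**The case against.** The case on the other side is substantial.

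- **The gap is narrow.** The event must be grade 3, non-serious, rated exactly possible, longer than 48 h and the first of its kind in the group, and the two-subject reading must apply. This stands, and it limits the size of the point.
- **The narrower notice rule may be deliberate**, since a rating of possible means the investigator thinks another cause more likely. That is conceivable, but 9.5.4 lets the same events count toward a hold, and notice by itself stops nothing.
- **Other safeguards exist.** All serious events reach the monitor within 24 h whatever their causality, and these include other important medical events by investigator judgment (9.2.3). Investigators can put dosing on hold (8.7, 9.5.4). An ad hoc SMC meeting can be called at any time (9.5.3). The monitor sits on the SMC, whose Charter sets members' duties (9.5.2). These narrow the gap but do not close it in the protocol text.

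Three stronger readings are tempting, and the documents support none of them.

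- A reader might infer that a hold could be missed. It could not on this account, because 9.5.4 counts the event whether or not the monitor has heard of it.
- A reader might infer that the monitor is barred from hearing of other grade 3 events, contrary to the review role in the same section. Section 9.5.1 states what must be notified and forbids nothing more.
- A reader might infer that the >48 h condition is an error because sentinels can be dosed 48 h apart. The condition is the same in both sections and may be a deliberate screen for transient reactions. Longer gaps are allowed, and earlier notice would enable only discretionary advice.

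**Conclusion.** The causality wording in 9.5.1 does not match 9.5.4 or the definition of related in 9.4.4, and it should be aligned. The consequence is late notice of one kind of event, and only if the holding rule needs two subjects.

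The effect is small. Five subjects remain to be dosed, and section 13.2 reports no grade 3 event in groups 1 to 4 (0 of 20). The rate after subcutaneous dosing is unknown, so no event probability is claimed. The conclusion rests on the protocol text alone, and the SMC Charter may already require wider notice.

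The timing result holds at the 48 h minimum, which Table 2 also lists as optimal. It supports an improvement rather than a correction.

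**What to change.** **Change to make.** In 9.5.1, insert the word possibly so that the causality terms read possibly, probably or definitely related. Keep grade 3 and the >48 h condition, so the notice rule matches 9.5.4. The cost is one word and perhaps a few more notifications.

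**Optional extra.** For subjects 1 and 2 of a group, ask for prompt notice to the monitor of any grade 3 event at least possibly related to TB31F, whatever its duration. The monitor could then advise before the next dose when the event is known by then. Leave the 9.5.4 threshold as it is and do not make dosing wait on the notice. In particular, add no step between subjects 3 to 5, who may be dosed an hour apart. The cost is again a few more notifications.
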